13.2.3.3 Assessment of Expectedness

Expected	An adverse reaction, the nature or severity of which is consistent with the applicable product information (e.g., Investigators' Brochure for an unapproved medicinal product).
Unexpected	An adverse reaction, the nature or severity of which is not consistent with information in the relevant source document (e.g., Investigators' Brochure for an unapproved medicinal product).

13.2.4 Reporting of SAEs

Once a Sponsor-Investigator becomes aware that an SAE has occurred in a study subject, he/she will assess the event and determine if it meets regulatory reporting requirements. The Investigator must also notify the reviewing Investigational Review Board (IRB) and site governance office (if required) of any SAEs according the guidelines of the IRB.

14. DATA ANALYSIS AND STATISTICAL CONSIDERATIONS

Data for this study will be entered into a REDCap database, which uses a MySQL database via a secure web interface with data checks used during data entry to ensure data quality. REDCap includes a complete suite of features to support HIPAA compliance, including a full audit trail, user-based privileges, and integration with the institutional LDAP server. The MySQL database and the web server will both be housed on secure servers operated by the University of Minnesota Academic Health Center's Information Systems group (AHC-IS). The servers are in a physically secure location on campus and are backed up nightly, with the backups stored in accordance with the AHC-IS retention schedule of daily, weekly, and monthly tapes retained for 1 month, 3 months, and 6 months, respectively. Weekly backup tapes are stored offsite. The AHC-IS servers provide a stable, secure, well-maintained, and high-capacity data storage environment, and both REDCap and MySQL are widely-used, powerful, reliable, well-supported systems. Access to the study's data in REDCap will be restricted to the members of the study team by username and password.

The general analytical approach for all endpoints will be descriptive in nature. No formal statistical hypothesis testing will be conducted. No p-values will be presented due to the small sample size of this study. Data analyses will be provided for all study subjects combined wherever appropriate.

For continuous variables, summary statistics will include number of subjects, mean, median, standard deviation, minimum, and maximum. For categorical variables, descriptive statistics will include number of subjects and percentages.

In regards to handling of missing data, there will be no imputation of missing values.

14.1 Analysis Populations

Safety Population: all subjects who receive at least 1 dose of study drug and who have at least one post-dosing safety evaluation. All safety endpoints, baseline characteristics, and demographic data will be summarized using the Safety Population.

Efficacy Evaluable Population: all subjects who receive all 3 doses of study drug and have a follow up blood draw for vitamin D levels, or discontinue prior to completing dosing due to a drug-related adverse event. Vitamin D level data will be analyzed using the Efficacy Evaluable Population.

14.2 Study Endpoints

The primary endpoint is to establish the change in vitamin D blood levels following 3 doses of treatment with vitamin D gel.

Secondary study endpoints include assessment of safety, including change in parathyroid hormone level and the number of subjects who have any skin rash and/or other skin reaction following treatment with the vitamin D gel.

14.3 Data Analysis

14.3.1 Subject Disposition

The number and percentage of subjects entering and discontinuing the clinical study will be presented. The reasons for discontinuation will also be summarized.

14.3.2 Demography and Baseline Characteristics

Demographic and baseline characteristics will be descriptively summarized using the Safety Population. Quantitative and/or categorical summaries will be presented for demographics and other baseline characteristics.

14.3.3 Treatment Exposure

Treatment exposure will be summarized. Measures of extent of exposure include the total number of doses per subject, cumulative dose per subject, and compliance (percent of target dose received per cycle). The reason(s) for dose(s) missed will also be summarized.

14.3.4 Safety Analyses

Safety parameters will be listed and summarized using standard descriptive statistics.

Adverse event terms will be coded using the Medical Dictionary for Regulatory Activities (MedDRA) and will be summarized by dose. Incidence of AEs occurring during the study will be summarized by system organ class (SOC) and preferred term. Adverse events will also be summarized by causality and grade. Serious adverse events and AEs leading to discontinuation of study treatment will be listed separately.

Additional analyses will be performed if warranted upon review of the data.

14.3.5 Analysis of Efficacy

The primary outcome will be the change in total Vitamin D following the topical application of 100,000IU Vitamin D3 weekly for three weeks.

14.4 Determination of Sample Size

A change from baseline of 10 $\mu\text{g/L}$ in total 25-OH Vitamin D levels in subjects with Vitamin D deficiency is thought to be a clinically relevant improvement. Assuming that the standard deviation for pre and post measures of total 25-OH Vitamin D is 4 $\mu\text{g/L}$, then the standard deviation of the difference is 5.6 $\mu\text{g/L}$ so 10 subjects should be adequate to show an effect size of 6.4 $\mu\text{g/L}$ with alpha of .05 and a power of 90%. However the standard deviation of the second measure is unknown since absorption may vary by individual. Assuming the standard deviation of the second measure increases to 12, then 20 subjects would be needed to detect an effect size of 10 $\mu\text{g/L}$. In order to be most conservative, 20 subjects will be treated in this proof-of-concept study.

ETHICS

14.5 Ethical Considerations

This study will be carried out according to the Declaration of Helsinki, the National Statement on Ethical Conduct in Human Research (2007) and the Notes for Guidance on Good Clinical Practice as adopted by the Australian Therapeutic Goods Administration (TGA; 2000) (CPMP/ICH/135/95) and the ICH GCP Guidelines²⁷.

14.6 Ethical Review Committee

The Protocol will be submitted for review to the University of Minnesota Investigational Review Board (IRB), and written approval will be obtained from both the IRB and Governance Office (as required), before subjects are recruited and enrolled. The Investigators will receive all the documentation needed for submitting the protocol to the IRB and/or Governance Office. A copy of the respective approval letters will be obtained before starting the study. If approval is suspended or terminated by the IRB or Governance Office, the Sponsor-Investigator will have responsibility for notifying the Food and Drug Administration.

It is the responsibility of the Investigator to report study progress to the IRB or Governance Office as required.

The Sponsor-Investigator, or his/her nominee, will be responsible for reporting any SAEs to the IRB as required.

14.7 Informed Consent

Before recruitment and enrollment into the study, each prospective subject will be given a full explanation of the nature and purposes of the study. Once the essential study information has been provided, and the Investigator is assured that the volunteer understands the implications of participating in the study, the subjects will be asked to give consent to participate in the study by signing the Informed Consent Form (ICF)/Patient information sheet. The consent form will be signed and dated by the appropriate parties. A notation that written informed consent has been obtained will be made on the subject's medical record and CRF. The completed consent form will be retained by the Investigator. A copy of the completed ICF will be provided by the Investigator to the subject.

15. STUDY CONDUCT

15.1 Regulatory Authorities

This study will be conducted under an Investigational New Drug (IND 110937).

15.2 Monitoring Procedures and Quality Assurance

The organization, monitoring, supply of study materials and quality assurance of the present clinical study is the responsibility of Innovative Pharmacy Solutions or its designee.

Monitoring may be conducted to ensure compliance with the protocol, ICH GCP and applicable regulatory requirements.

In order to ensure the accuracy of data, direct access to source documents by the representatives of Innovative Pharmacy Solutions, Inc. and regulatory authorities is mandatory.

The Investigator is required to submit to the Reviewing IRB, annual (or more frequent if requested) reports of the study.

15.3 Curriculum Vitae

A current, signed and dated Curriculum Vitae for all study staff will be provided and maintained in the files at Innovative Pharmacy Solutions, Inc. (or designee). A Staff Signature List will be maintained at each Investigator's site.

15.4 Investigator Responsibilities

Except where the Principal Investigator's signature is specifically required, it is understood that the term 'Investigator' as used in this Protocol and on the CRFs refers to the Principal Investigator or an appropriately qualified member of the staff that the Principal Investigator designates to perform specified duties of the Protocol. The Principal Investigator is ultimately responsible for the conduct of all aspects of the study.

Each Investigator will comply with the local regulations regarding clinical trials and the Investigator responsibilities outlined in the ICH GCP guidelines.

15.5 Emergency Contact with Investigators

All subjects will be provided with a Participant Emergency Contact Card with contact details of whom to contact in the case of an emergency.

15.6 Notification of Primary Care Physician

With the consent of the subject, it is the Investigator's responsibility to notify the primary care physician of the subjects' involvement in the study, provided that such a physician can be identified for the subject. A letter will be sent to the physician stating the nature of the study, treatments, expected benefits or AEs and concomitant drugs to be avoided. A copy shall be retained by the study site.

15.7 Protocol Compliance

The instructions and procedures specified in this protocol require diligent attention to their execution. Any subject treated in a manner that deviates from the protocol, or who is enrolled into the study but is not qualified according to the Protocol may be ineligible for analysis and thereby compromise the study.

Only when an emergency occurs that requires a departure from the Protocol for an individual will there be such a departure. The nature and reasons for the Protocol violation/deviation shall be recorded in the CRF.

The Investigator and designees will comply with all applicable federal, state and local laws.

15.8 Termination of the Study

The Sponsor-Investigator reserves the right to terminate the clinical study at any time. Reasons for termination may include, but are not limited to, the following:

- the incidence or severity of AEs in this study
- serious or persistent noncompliance by the Investigator with the protocol, clinical research agreement, or applicable regulatory guidelines in conducting the study
- IRB decision to terminate or suspend approval for the investigation or the Investigator
- Investigator request to withdraw from participation

In addition the Sponsor-Investigator reserves the right to discontinue the study prior to inclusion of the intended number of subjects, but intends only to exercise this right for valid scientific or administrative reasons.

After such a decision, the Investigator must contact all participating subjects promptly, and written notification must be sent to the Reviewing IRB and relevant Governance Offices (as required).

16. ADMINISTRATIVE CONSIDERATIONS

16.1 Protocol Amendments

Protocol modifications that impact on subject safety or the validity of the study will be approved by the IRB. If a Protocol amendment requires changes to the Informed Consent Form, the revised Informed Consent Form, prepared by the Investigator, must be approved by the IRB and site governance offices (as required).

Once the final Protocol has been issued and approved by the Sponsor-Investigator and the authorized signatories, it shall not be informally altered. Protocol amendments are alterations to a legal document and have the same legal status. Therefore, they must pass through appropriate steps before being implemented. In general, any important change that theoretically increases risk to subjects constitutes an amendment.

It is the responsibility of the Investigator to submit the amendment to the IRB for their approval; written approval should be obtained. The original signed copy of amendments will be kept in the Study File with the original Protocol. It should be noted that where an amendment to the Protocol substantially alters the study design or the potential risks to the subjects, each subject's consent to continue participation should be obtained.

16.2 Archiving of Records

All source documents, CRFs and trial documentation will be kept by the Investigator for the appropriate retention period as stipulated by local regulations and ICH-GCP.

16.3 Study Report

The Sponsor-Investigator or designee will produce the clinical study report at the completion of the study. In addition, it is intended that the outcome of the study will be submitted for publication in appropriate peer review journals and scientific meetings, as accepted.

## **1. DATA ANALYSIS AND STATISTICAL CONSIDERATIONS**

Data for this study will be entered into a REDCap database, which uses a MySQL database via a secure web interface with data checks used during data entry to ensure data quality. REDCap includes a complete suite of features to support HIPAA compliance, including a full audit trail, user-based privileges, and integration with the institutional LDAP server. The MySQL database and the web server will both be housed on secure servers operated by the University of Minnesota Academic Health Center's Information Systems group (AHC-IS). The servers are in a physically secure location on campus and are backed up nightly, with the backups stored in accordance with the AHC-IS retention schedule of daily, weekly, and monthly tapes retained for 1 month, 3 months, and 6 months, respectively. Weekly backup tapes are stored offsite. The AHC-IS servers provide a stable, secure, well-maintained, and high-capacity data storage environment, and both REDCap and MySQL are widely-used, powerful, reliable, well-supported systems. Access to the study's data in REDCap will be restricted to the members of the study team by username and password.

The general analytical approach for all endpoints will be descriptive in nature. No formal statistical hypothesis testing will be conducted. No p-values will be presented due to the small sample size of this study. Data analyses will be provided for all study subjects combined wherever appropriate.

For continuous variables, summary statistics will include number of subjects, mean, median, standard deviation, minimum, and maximum. For categorical variables, descriptive statistics will include number of subjects and percentages.

In regards to handling of missing data, there will be no imputation of missing values.

### **1.1 Analysis Populations**

*Safety Population:* all subjects who receive at least 1 dose of study drug and who have at least one post-dosing safety evaluation. All safety endpoints, baseline characteristics, and demographic data will be summarized using the Safety Population.

*Efficacy Evaluable Population:* all subjects who receive all 3 doses of study drug and have a follow up blood draw for vitamin D levels, or discontinue prior to completing dosing due to a drug-related adverse event. Vitamin D level data will be analyzed using the Efficacy Evaluable Population.

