8.3 Criteria for Withdrawal

A subject has the right to withdraw fully or partially from the study at any time and for any reason without prejudice to his or her future medical care by the physician or at the institution.

Withdrawal of full consent for a study means that the subject does not wish to receive further investigational treatment and does not wish to or is unable to continue further in study participation. Subject data up to withdrawal of consent will be included in the analysis of the

study. The Investigator will discuss with the subject appropriate procedures for withdrawal from the study. Withdrawal of partial consent from a study means that the subject does not wish to take investigational product or other protocol-required therapy any longer but is still willing to collaborate in providing further data by continuing on study. Should a subject request or decide to withdraw from the study, all efforts will be made to complete and report the observations as thoroughly as possible up to the date of withdrawal. All information should be reported on the applicable case report form (CRF). Reasons for removal from protocol-required treatment or observation might include:

- partial/full withdrawal of consent
- administrative decision by the Sponsor-Investigator
- pregnancy
- ineligibility
- significant protocol deviation
- subject noncompliance
- adverse event, including rash or other skin reaction
- Death

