12.1 Vitamin D Levels

Assessments of serum 25-OH vitamin D levels (D2 and D3) will be done and on Day 0, 7, 14, and 21. Venous blood draws will be performed by a trained University of Minnesota Physicians (UMP) technician and delivered to HealthEast laboratory for analysis.

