13. ASSESSMENT OF SAFETY

13.1 Safety Assessments

13.1.1 Skin Rash or Other Reaction

An assessment of each subject's skin will be performed on Days 7, 14 and 21 using the following scoring system for topical irritation developed per FDA guidance:

Basic Score: Description:

- 0 No visible reaction
- 0.5 Doubtful or negligible erythema reaction
- 1.0 Mild or just perceptible macular erythema reaction in a speckled/follicular, patchy or confluent pattern (slight pinking)
- 2.0 Moderate erythema reaction in a confluent pattern (definite redness)
- 3.0 Strong or brisk erythema reaction that may spread beyond the test site

Supplemental Scores: Description: Label:

- 0.5 Edema E
- 0.5 Papules P
- 0.5 Vesicles V
- 0.5 Bullae B

Supplemental scores will be added to the basic scores if the associated symptoms are present. The final score will be the sum of the basic and supplemental scores.

As part of the general safety assessment, dermal irritation will be evaluated by the Investigator or designated research staff using the outlined scale. The likelihood of allergic reaction not manifested as a dermal irritation is extremely low. Given that all the ingredients used to make the topical vitamin D gel are considered GRAS, we do not anticipate non-local allergic reactions. In the event that a non-dermal allergic reaction occurs, standard medical procedures utilized for such situations will be followed.

If a subject develops a dermal response of 1.5 up to 2.5, he or she will be given the option to permanently discontinue the study treatment and withdraw from the study, or to allow sufficient time for the rash to resolve before he or she reinitiates the phase of the study he or she was in at the time that the rash developed. If a participant develops a dermal response of 2.5 or greater, he or she will be required to permanently discontinue the study treatment and he or she will be withdrawn from the study. In both cases, the study participant will be encouraged to seek medical care from his or her primary care physician. In addition, we will ask subjects who decide to withdraw from the study to return for their next scheduled blood draw, as per protocol. We will also follow up with any study participant who withdraws from the study due to AE occurrence through telephone contact at 1 week intervals until the AE resolves.

All other adverse events will be assessed by self-report from subjects.

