We will initially administer 100,000 units topically to subjects, and check serum Vitamin D and calcium levels one week later. Dosing will be discontinued if a patient achieves a Vitamin D level of greater than normal (> 90 ng/ml) or if serum calcium rises above normal (> 10.2 mg/dl). Additional doses of 100,000 units will be administered on days 7 and 14. The outcome of interest will be the effect on total serum Vitamin D at 21 days. Although a change in calcium is unlikely, calcium will be monitored for safety.

Vitamin D may alter glucose values and improve glucose control in individuals with diabetes²⁶. Although individuals with diabetes will not be excluded, we will instruct any subjects with diabetes to more closely monitor glucose values during the course of the study.

Parathyroid hormone will be measured at baseline and on Day 21 to determine if vitamin D correction changes the level of this metabolic calcium regulatory hormone.

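### The primary outcome is written for a weekly dose one third of that in the protocol's design section; a narrower gap affects who stays in the vitamin D analysis

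*SAP*

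**What the plan says.** **Dose.** SAP 1.3.5 and Protocol 14.3.5 describe the primary outcome as the change in total vitamin D after 100,000 IU applied weekly for three weeks. Protocol 13.1.1 starts subjects on 100,000 units and continues: "Additional doses of 100,000 units will be administered on days 7 and 14". The same paragraph holds the laboratory criteria: "Dosing will be discontinued if a patient achieves a Vitamin D level of greater than normal (> 90 ng/ml) or if serum calcium" rises above 10.2 mg/dl.

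The Synopsis, the product description in Protocol 5.1, the last paragraph of 5.2.2, the objectives in 6, the design in 7.1 and the text of 10.2 all give 300,000 IU per dose, as two applicators of 150,000 IU. The sample labels in 10.2 show 50,000 IU in 0.25 ml. SAP 1.3.3 measures compliance as a percentage of the target dose and does not state the target.

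**Population.** SAP 1.1 and Protocol 14.1 use one set for vitamin D data. It takes "all subjects who receive all 3 doses of study drug and have a follow up blood draw for vitamin D levels", and also those who "or discontinue prior to completing dosing due to a drug-related adverse event". SAP 1 rules out imputation. The SAP names no day for the primary outcome; Protocol 13.1.1 does: "The outcome of interest will be the effect on total serum Vitamin D at 21 days".

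**The concern.** The primary outcome should describe the treatment that subjects receive. Here the sections that define the outcome and those that define the design disagree by a factor of three. The safety paragraph and the labels side with the outcome sections, so this is not one stray figure. A report that follows SAP 1.3.5 literally would attribute the result to a regimen that Protocol 7.1 does not plan. Compliance could not be computed without choosing between sections, and the laboratory criteria would stand in a paragraph written for a different dose from the one in the design.

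The second issue is smaller. A laboratory stop ends dosing before dose 3, and no section says whether it counts as a drug-related adverse event. Whether that subject's observed values are analysed then depends on a coding decision made after the value is seen. For a vitamin D stop, the exclusion would be on the primary variable itself. The subject would not be replaced, because Protocol 8.4 ends replacement at the Day 7 draw.

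**Working it through.** **1. Doses side by side**

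| Place | Per dose (IU) | Three doses (IU) |
|---|---|---|
| SAP 1.3.5; Protocol 14.3.5 | 100,000 | 300,000 |
| Protocol 13.1.1 | 100,000 | 300,000 |
| Protocol 10.2, sample labels | 2 × 50,000 = 100,000 | 300,000 |
| Synopsis; Protocol 5.1, 5.2.2, 6, 7.1, 10.2 text | 2 × 150,000 = 300,000 | 900,000 |

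Ratio of totals: 900,000 / 300,000 = 3.

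The gel strength is not in dispute. The formula in Protocol 10.1 puts 20 g at 1,000,000 IU/g into 100 g, which is 200,000 IU/g and matches the label's 200,000 IU/mL (taking 1 g as about 1 mL). At that strength 0.75 mL holds 150,000 IU and 0.25 mL holds 50,000 IU, so the conflict lies in the quantity per syringe. The Synopsis contains both: 0.75 g per applicator in the drug description and 0.25 mL in the application instructions. Protocol 7.1, 9.2 and 10.3 have 0.75 mL.

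Compliance under SAP 1.3.3:
- given 3 × 300,000 IU against the SAP 1.3.5 dose: 900,000 / 300,000 = 300%
- given 3 × 100,000 IU against the Protocol 7.1 dose: 300,000 / 900,000 = 33%

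**2. The plan's own variability (SAP 1.4)**

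- First scenario: √(4² + 4²) = 5.66, stated as 5.6, so zero correlation is assumed.
- Second scenario: √(4² + 12²) = 12.65. A paired t test (two-sided 0.05, 90% power, difference 10) needs 19 subjects, and 20 give 91.8%. The stated 20 reproduces.

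**3. Chance of a vitamin D stop before dose 3**

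Assumptions: baseline no higher than 20, so a rise above 70 is needed; SD of change 12.65; normal changes; a linear rise over three doses; each visit's result known before that visit's dose.

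- Final mean rise 10: Day 7 z = (70 − 3.33)/12.65 = 5.27, p = 6.8 × 10⁻⁸. Day 14 z = (70 − 6.67)/12.65 = 5.01, p = 2.8 × 10⁻⁷. Across 20 subjects: 20 × (sum) = 6.9 × 10⁻⁶.
- Final mean rise 30: z = 4.74 and 3.95, p = 1.05 × 10⁻⁶ and 3.86 × 10⁻⁵. Across 20 subjects: 7.9 × 10⁻⁴, or 0.08%.
- If results are not back before the same visit's dose, only the Day 7 result can act: 1.4 × 10⁻⁶ and 2.1 × 10⁻⁵.

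These are far tails, and SAP 1.4 itself calls the second SD unknown. With an SD 1.5 times as large (1.5 × 12.65 = 18.97), the same sums give about 1.3% (z = 3.51 and 3.34) and 10% (z = 3.16 and 2.64).

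**4. Calcium stops**

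The documents give no rate. If the per-subject rate were 2%, 5% or 10%, the chance of at least one in 20 would be 33%, 64% or 88% (1 − (1 − rate)²⁰). Only those not coded as drug-related adverse events would be lost.

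**5. What one lost subject does**

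- Standard error of the mean: 12.65/√20 = 2.83 becomes 12.65/√19 = 2.90.
- Mean: if the subject's change differs by d from the average of the other 19, including that subject moves the mean by d/20; d = 20 µg/L gives 1.0 µg/L. The Day 21 value after a stop is unknown, so neither the sign nor the size of d can be stated.

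**The case against.** On the population, much of the defence stands. Protocol 13.2.1 defines adverse events broadly, and 13.2.3.1 allows a purely diagnostic finding to be graded mild. A calcium value that rises above normal and stops dosing fits, and would usually enter the set by the adverse-event route. What remains is a calcium stop judged unrelated, or a vitamin D value above 90 ng/ml.

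A reader might infer that no data rule exists after a laboratory stop. The documents do not support that. Protocol 13.1.1 stops dosing, not participation; 7.2 and Table 1 follow subjects to Day 21; and without imputation, a subject with no Day 21 value cannot enter a Day 21 mean. The request in 13.1.1, "we will ask subjects who decide to withdraw from the study to return for their next scheduled blood draw, as per protocol", concerns withdrawals after a skin reaction.

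A reader might also see a contradiction with Protocol 8.3: "Subject data up to withdrawal of consent will be included in the analysis". That sentence refers to the analysis of the study as a whole. The disposition, exposure and safety summaries can satisfy it.

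It can fairly be added that the endpoint is change after three doses, so a completer set is defensible. That supports showing completers, but does not settle how a laboratory stop is classified.

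On the dose there is no good defence. One could say that SAP 1.1 names no dose, so the same subjects are analysed either way. That is true, but it leaves the outcome definition and the compliance target unresolved.

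**Conclusion.** The dose statement is wrong as written. The primary outcome and the design section differ threefold (300,000 against 900,000 IU in total), and the sample labels conflict with the text beside them. This rests only on the passages themselves.

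A reader might infer which regimen is intended. Protocol 5.2.2 reports three early candidates given 300,000 units over three weeks and then plans three doses of 300,000 IU, which could suggest that the 100,000-unit text is left over. The labels point the other way, and the documents do not settle it. Nor do they support inferring that subjects would be wrongly dosed, or that the early candidates would be pooled with the 20: no section says either.

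The population gap is real but minor. On the planning SD a vitamin D stop before dose 3 is very unlikely (about 7 × 10⁻⁶ to 0.08% across 20 subjects), although this depends strongly on the assumed SD. Calcium stops have no planning rate and would mostly qualify as adverse events. It is tempting to say that the gap removes the best responders and pulls the mean down. The documents do not support a direction or a size, because the Day 21 value after a stop is unknown. The argument is for an unambiguous rule fixed before the data are seen.

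**What to change.** **Dose.** Reconcile every dose-bearing passage: the Synopsis (including its 0.25 mL instruction), Protocol 5.1, 5.2.2, 6, 7.1, 10.2 (text and labels), 13.1.1, 14.3.5 and SAP 1.3.5. The primary outcome, the compliance target in SAP 1.3.3 and the safety paragraph should then refer to one regimen, with the target dose stated in SAP 1.3.3. The choice of dose belongs to the sponsor-investigator. The cost is editing plus the amendment route in Protocol 16.1; no new data are needed.

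**Population.** Add one sentence to SAP 1.1 and Protocol 14.1: subjects whose dosing is stopped under the 13.1.1 laboratory criteria remain in the efficacy set with their observed draws, whether or not the stop is coded as an adverse event. Name Day 21 in the SAP as the primary time point, with no carry-forward. Show the three-dose completers alongside.

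The cost is a few lines and one extra table. The downside is that the set mixes subjects with one, two and three doses, as it already does for adverse-event stops; the completer table gives the strict three-dose reading.
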